#### Neurotoxicity

In the event of significant toxicity (extensive weakness, severe paresthesia, severe ileus), VBL may be temporarily discontinued and resumed at 50% dose when toxicity resolves. Contact the local study coordinator before discontinuing VBL. Increase to maximum tolerated dose (not exceed protocol dose) as soon as possible.

#### Oral 6-mercaptopurine and oral methotrexate

if neutrophil count falls below 500/ $\mu$ l, treatment will be held until recovery above these levels and then resumed as tolerated. If neutrophil count falls below 500/ $\mu$ l on >2 occasions during continuation, discontinue TMP/SMZ and decrease dose of 6-MP or

MTX by 25% on alternating basis upon resumption of therapy. Begin by reducing the 6-MP dose. Should therapy be withheld for myelosuppression or elevated transaminase, resume therapy at the correct point chronologically.

## 10 ASSESSMENT OF TREATMENT RESPONSE

In contrast to leukemia or other malignancies the terms “remission” or “relapse” should be avoided. In accordance with the nature of LCH the following definitions should be applied to judge the effect of treatment.

### 10.1 DEFINITION OF DISEASE STATE

NON ACTIVE DISEASE (NAD)	no evidence of disease	resolution of all signs or symptoms
	regressive disease	regression of signs or symptoms, no new lesions
ACTIVE DISEASE (AD)	stable disease	persistence of signs of symptoms, no new lesions
	progressive disease*	progression of signs or symptoms and/or appearance of new lesions

### 10.2 DEFINITION OF RESPONSE CRITERIA

There are three categories of response

BETTER	complete resolution	NAD
	regression	AD better
INTERMEDIATE	mixed	new lesions in one site, regression in another site
	stable	unchanged
WORSE	progression*	

\*in isolated bone disease progression is defined as appearance of new bone lesions or

lesions in other organs

### 10.3 RESPONSE EVALUATION

Please send the follow up evaluation sheet to the study subcenter as soon as possible after the evaluation (fax or e-mail).

Clinical status and performance

Blood count and differential

Requirement of blood products

Liver and spleen size

Liver enzymes and function tests

HR-CT and pulmonary function tests (if age-appropriate) for patients with lung disease

Skeletal radiograph of lesional sites only

MRI of the brain in patients with “CNS-RISK” lesions or intracranial lesions

Spinal MRI in patients with vertebral lesions

Histological proof of AD or NAD may be required in specific sites

#### 10.3.1 Group 1: “RISK PATIENTS”

Any treatment decision must be based on the response in “RISK ORGANS” (i.e.R.O.)

INTERVAL	EVALUATION	RESPONSE	THERAPY
week 6	after initial treatment course 1	NAD	continuation treatment
		better	initial treatment course 2
		intermediate	initial treatment course 2
		worse	salvage (see appendix)
week 12	after initial treatment course 2	NAD	continuation treatment
		better	continuation treatment
		intermediate	salvage (see appendix)
		worse	salvage (see appendix)

week 24 or any time in case of event	during continuation treatment	NAD, better	continuation treatment
		intermediate without R.O. intermediate with R.O.	continuation treatment  salvage (see appendix)
		worse without R.O.	arm A: re-start initial treatment arm B arm B: salvage (see appendix)
		worse with R.O.	salvage (see appendix)
month 12	end of continuation treatment	NAD	STOP (in case of persistent signs of disease activity, please discuss with local coordinator)

### 10.3.2 Group 2 “LOW RISK” patients

Please send the follow up evaluation sheet to the study subcenter IMMEDIATELY after the evaluation at week 6 (fax or e-mail) to have the randomization for the duration of continuation treatment performed!

Interval	Evaluation	RESPONSE	CONTINUE
week 6	after initial treatment course 1	NAD better	continuation treatment randomization: LR 6 or LR 12
		intermediate	initial treatment course 2
		worse	initial treatment course 2
week 12	after initial treatment course 2	NAD better	continuation treatment
		intermediate	continuation treatment
		worse	discuss with local coordinator
week 7 or 13- 23	during continuation treatment	NAD, better	continuation treatment
		intermediate	continuation treatment
		worse	discuss with local coordinator

month 6	end of continuation treatment	NAD better	LR 6 STOP LR 12 continuation treatment
		intermediate	continuation treatment
		worse	re-start initial treatment arm B
month 6-12	during continuation treatment LR 12	NAD better	continuation treatment
		intermediate	continuation treatment
		worse	re-start initial treatment arm B
month 12	end of continuation therapy LR 12		STOP (in case of persistent signs of disease activity, please discuss with local coordinator)

### 10.3.3 Group 3 patients with “MFB” or “SPECIAL SITES”

Brain MRI (and/or CT scans) or spinal MRI must be performed to assess the treatment response in these critical sites. In case of residual “CNS-RISK” lesions on MRI treatment must not be stopped. A biopsy of such lesions to rule out residual active disease should be considered.

Interval	Evaluation	RESPONSE	CONTINUE
week 6	after initial treatment course 1	NAD better	continuation treatment
		worse	initial treatment course 2 (risk patients arm A)
week 12	after initial treatment course 2	NAD better	continuation treatment
		worse	discuss with local coordinator
week 7 or 13-23	during continuation treatment	NAD better	continuation treatment
		worse	discuss with local coordinator

month 6	after continuation treatment	NAD better	STOP (in case of clear regression stop therapy, repeat MRI after 3 months, in case of significant residual tumor consider biopsy and discuss with local coordinator)
---------	------------------------------	------------	---

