### **5.3 GROUP 3 - SINGLE SYSTEM “MULTIFOCAL BONE DISEASE” AND LOCALIZED “SPECIAL SITE” INVOLVEMENT**

Patients with multifocal bone disease, i.e. lesions in 2 or more different bones;

Patients with localized special site involvement, like “CNS-RISK” lesions with intracranial soft tissue extension or vertebral lesions with intraspinal soft tissue extension;

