### **6.2.3 To assess acute and late treatment toxicity**

## **6.3 GROUP 3: SINGLE SYSTEM MULTIFOCAL BONE AND LOCALIZED “SPECIAL SITES”**

### **6.3.1 To reduce morbidity**

i.e. the rate of reactivation and permanent consequences (as compared to the historical control group of the DAL HX 83/90 and LCH I and II studies).

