## **9.3 GROUP 3: “MULTIFOCAL BONE DISEASE” AND “SPECIAL SITES”**

Treatment consists of an initial treatment of 6 weeks and a continuation treatment. A second course is given only to patients with progressive disease. The overall therapy duration is 6 months.

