### **9.3.2 Continuation treatment**

(starting after initial treatment at day 1 of week 7 in pts who are NAD after course 1 of initial treatment or at day 1 of week 13 in patients who are NAD or AD-better after course 2 of initial treatment)

Pulses of oral prednisone PDN 40mg/m^2 in 3 doses, day 1-5 q 3 weeks, starting at day 1 of week 7 in patients NAD after course 1 or at day 1 of week 13 in patients NAD or AD better after course 2 until the end of month 6 from therapy start.

Vinblastine (VBL) 6mg/m^2 i.v. bolus, day 1 q 3 weeks, starting at day 1 of week 7 in patients NAD after course 1 or at day 1 of week 13 in patients NAD or AD better after course 2 until the end of month 6 from therapy start.

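### Section 10.3.3 gives opposite instructions at month 6 for a Group 3 patient whose CNS-RISK lesion has clearly regressed but is still visible on MRI

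*Protocol*

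**What the plan says.** Group 3 includes patients with localised special-site disease, described in Protocol section 5.3 as CNS-RISK "lesions with intracranial soft tissue extension or vertebral lesions with intraspinal soft tissue extension". Several places bear on when their treatment ends:

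- **Section 10.3.3, text above the table.** With residual CNS-RISK "lesions on MRI treatment must not be stopped". The next sentence asks that a biopsy be considered, to exclude residual active disease.
- **Section 10.3.3, month 6 row.** For NAD or better the instruction is STOP. The bracket adds "in case of clear regression stop therapy, repeat MRI after 3 months" and then "in case of significant residual tumor consider biopsy and discuss with local coordinator".
- **Section 9.3.** "The overall therapy duration is 6 months".
- **Section 9.3.2.** Prednisone pulses and vinblastine run, for patients who are NAD or "AD better after course 2 until the end of month 6 from therapy start".
- **Section 11.** Where residual active disease is evident when protocol therapy ends, biopsy is recommended and the case goes to the local coordinator.
- **Section 13, first-year follow-up after therapy has stopped.** Brain MRI for CNS risk lesions continues every three months until there is no residual mass or the findings are stable.

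**The concern.** The sentence above the table is an unconditional prohibition, and the row below it is an order to stop. A site treating a child with a shrinking but visible CNS-RISK lesion at month 6 departs from an explicit instruction whichever one it follows. Compliant sites could therefore treat like patients for different lengths of time.

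The protocol itself singles these patients out. Section 2.3.2.1 attributes to CNS-RISK lesions about a three-fold risk of diabetes insipidus. The Group 3 goal in section 6.3.1 is to reduce reactivation and permanent consequences, "as compared to the historical control group of the DAL HX 83/90 and LCH I and II studies". If duration varies by site within this subset, what is set beside the historical series is, for these patients, not one defined regimen.

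**Working it through.** No figure is at issue. The protocol states no sample size for Group 3, and the point rests on no event count, power or error rate. The check follows one patient through the text.

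**1. Can such a patient exist?** Yes. Section 5.3 admits patients with a localised CNS-RISK lesion. Section 10.1 defines regressive disease as "regression of signs or symptoms, no new lesions" and lists it under active disease, apart from the category in which all signs have resolved. Section 10.2 labels it AD better. A patient can therefore be better while a lesion remains on MRI.

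**2. What does each instruction require at month 6, if the lesion has clearly regressed but is visible?**

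| Place | Trigger | Instruction |
|---|---|---|
| 10.3.3, text above table | residual CNS-RISK lesion on MRI | do not stop; consider biopsy |
| 10.3.3, month 6 row | NAD or better | STOP |
| 10.3.3, bracket, first part | clear regression | stop; repeat MRI after 3 months |
| 10.3.3, bracket, second part | significant residual tumour | consider biopsy; discuss with local coordinator |
| 9.3 and 9.3.2 | all Group 3 | planned end at month 6 |
| Section 11 | residual active disease at end of protocol therapy | biopsy recommended; discuss |

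The patient meets the first three triggers together. The first line forbids what the second and third order.

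**3. Does a time limit separate the lines?** The prohibition has none. Reading it as a ban only on stopping before month 6 does not work, because month 6 is the only stop point in the Group 3 table.

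**4. Does the term for residual disease separate them?** The text above the table is triggered by any residual CNS-RISK lesion on MRI. The bracket uses significant residual tumour. Neither term is defined against the other. A residual lesion that has clearly regressed and is not judged significant goes to the stop branch of the bracket but stays under the prohibition.

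**5. Does another section rank the instructions?** Section 11 adds biopsy and discussion but does not say whether therapy ends meanwhile. Section 13, headed as follow-up after therapy has stopped, plans MRI until a residual mass has gone or is stable. It thus presupposes patients off therapy with a residual mass, which the prohibition does not allow. How far that table cell extends across the patient columns is unclear in the extracted text, so it counts only as support. The contradiction is complete within 10.3.3 without it.

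**The case against.** The strongest reply is that this is one sentence against one bracket, in a setting where the protocol plainly intends individual review. Much of that is fair.

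- **Sections 9.3 and 9.3.2 are not a second contradiction.** A reader might count them as one. They state a planned duration, and a response table may modify a plan. Group 1 is built the same way: 9.1 sets 12 months, and the month 12 row sends persistent activity to discussion. What stands is that 9.3 and 9.3.2 give no exception and so do not resolve the conflict.
- **There is a route for residual disease.** Section 11 and the second part of the bracket send it to biopsy and the local coordinator, so it would be wrong to say that the protocol offers nothing. For significant residual tumour, the bracket gives that route and not a plain stop. But clear regression is an outright stop with no biopsy condition.
- **A visible lesion need not be active.** The biopsy sentence draws that distinction. It does not say that a negative biopsy lifts the prohibition, whose trigger is the MRI finding.
- **Treatment duration is not uncertain for all of Group 3.** A reader might infer this, but patients with only multifocal bone disease or only vertebral lesions are outside the sentence.
- **No hypothesis test is spoiled.** Section 7 calls Group 3 a pilot, and section 16 gives it no design, primary endpoint, test or sample size. Section 6.3.1 states a goal against historical controls. The loss is in how clearly the pilot's regimen can be described.

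**Conclusion.** The contradiction is real and sits within section 10.3.3. It applies to Group 3 patients with a CNS-RISK lesion that, at month 6, has clearly regressed (AD better) but is still visible on MRI. For them the protocol orders treatment both to stop and not to stop, and no section says which instruction governs.

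Its reach is limited. It concerns a subset of a non-randomised pilot. The documents do not give the share of patients in that subset, and the conclusion does not depend on it. Both randomised comparisons (Group 1, arm A against arm B; Group 2, LR 6 against LR 12) are unaffected. The conclusion rests only on the reading that AD better can coexist with a visible lesion, which 10.1 and 10.2 support. It takes no position on which instruction is clinically right.

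**What to change.** 1. The sponsor's clinicians should reconcile the sentence above the 10.3.3 table and the month 6 row into one rule for a CNS-RISK lesion that has regressed but is still visible. Which rule applies is for them to decide.
2. Use one defined term in both places instead of the two now used for residual lesions and significant residual tumour.
3. Align 9.3, 9.3.2, section 11 and the section 13 follow-up table with that rule, by cross-reference where this is enough.
4. In the Group 3 report, describe how many patients were treated beyond month 6 and for how long. Do not compare reactivation or permanent consequences between those treated for six months and those treated longer. Duration would depend on the response at month 6, so the groups would differ in prognosis. Counted from the start of therapy, the longer-treated group must also have reached month 6 still on treatment, which builds in immortal time.

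The cost is a wording amendment to one sentence and one table row, a few cross-references and one descriptive line in the report. Sample size, randomisation and the Group 1 and Group 2 analyses do not change.

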## 11 OFF STUDY CRITERIA

In case of progression in “RISK organs” after initial treatment course 1 or course 2 switch to salvage (see appendix).

In case of evidence of residual active disease at the end of protocol therapy a biopsy of residual lesions to rule out persistent active disease is recommended, and the individual case should be discussed with the local co-ordinator.

If you have any questions regarding salvage therapy, please contact the local coordinator or the study reference center.

## 12 AUTOPSY

Autopsy is to be encouraged for fatal cases. A set of unstained slides (5-10) or blocks should be submitted to the regional study pathologist.

## 13 FOLLOW UP INVESTIGATIONS AFTER STOP OF THERAPY

	FOLLOW UP		
	With Risk Organ involvement	Without Risk Organ involvement	Multifocal bone involvement, special site
1. year			
Clinical examination	6 weekly	6 weekly	3 monthly
Height, weight, pubertal status	6 monthly	6 monthly	6 monthly
Lab-examinations Blood count, ESR, liver (renal function )tests, urine osmolality	3 monthly	3 monthly	6 monthly
Radiographs of bone lesions	3 monthly until signs of regression (or as clinically indicated)	3 monthly until signs of regression (or as clinically indicated)	3 monthly until signs of regression (or as clinically indicated)
HR-CT, pulmonary function tests (in case of pulmonary involvement)	6-monthly		
Sonography in pts with liver involvement	6-monthly		
Brain MRI in pts with DI or other endocrinopathies, in pts with CNS risk lesions	yearly,  3 monthly until no residual mass lesions or stable findings		
Neuropsychometric assessment (in case of CNS involvement)	yearly	yearly	yearly

2.- 5. year			
Clinical examination* *more frequently when clinically indicated	6 monthly*	6 monthly*	6 monthly*
Height, weight, pubertal status	6-monthly	6-monthly	6-monthly
Lab-examinations Blood count, ESR, liver and renal function tests, urine osmolality	6 monthly (or as clinically indicated)	6 monthly (or as clinically indicated)	6 monthly (or as clinically indicated)
Radiographs of bone lesions	only in case of suspected lesions	only in case of suspected lesions	only in case of suspected lesions
HR-CT and pulmonary function tests in pts with lung involvement	6 monthly (or as clinically indicated)	-	-
Brain MRI in pts with DI or other endocrinopathies, with CNS risk lesions	yearly (or more frequently when indicated)	yearly (or more frequently when indicated)	yearly (or more frequently when indicated)

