### **9.2.1.3 Continuation treatment**

The overall therapy duration is 6 months for Arm LR 6 or 12 months for Arm LR 12 .

Pulses of oral prednisone PDN 40mg/m^2 in 3 doses, day 1-5 q 3 weeks, starting at day 1 of week 7 in patients NAD after course 1 or at day 1 of week 13 in patients NAD or AD better after course 2 until the end of month 6 or 12 from therapy start.

Vinblastine (VBL) 6mg/m^2 i.v. bolus, day 1 q 3 weeks, starting at day 1 of week 7 in patients NAD after course 1 or at day 1 of week 13 in patients NAD or AD better after course 2 until the end of month 6 or 12 from therapy start.

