#### **16.3.1.2 Group 2 “LOW RISK” patients:**

Reactivation (=progression in any organs) and death will be considered as events for the calculation of Reactivation Free Survival. The interval will start 6 months after therapy start, i.e. the time point when half of the patients are intended stop the continuation therapy (Arm LR6) whereas patients from the other randomized arm (Arm LR12) will further receive 6 months of continuation therapy. This means, randomized patients with reactivations within the first 6 months after randomization will not be included in the analyses. For censored patients the interval will be calculated until the date of the last response evaluation.

The proportion of reactivation free survival will be estimated according to the method of Kaplan-Meier and confidence intervals according to Dorey and Korn will be given for the reactivation free survival rate after 2 and 3 years. The primary statistical evaluation of the treatment effect will be done by log rank-test.

As a secondary aim the question whether a prolonged therapy can slow down the speed of reactivation will be considered. Retrospective data from LCH-I and LCH-II and the DAL-studies indicate that the hazards between 6 and 12 months of continuation therapy are proportional and constant in time (i.e. exponentially distributed reactivation free survival times). Therefore, a Weibull accelerated failure time model will be fitted to evaluate an acceleration factor. Moreover, a time dependent Cox regression model will be performed.

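### Group 2 follow-up visits are counted from the stop of therapy, which differs by arm, so reactivation is looked for on different calendars in LR 6 and LR 12 within the primary interval; the effect is modest and its direction is not fixed

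*Protocol*

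**What the plan says.** Section 9.2.1.3 sets the randomised contrast: "The overall therapy duration is 6 months for Arm LR 6 or 12 months for Arm LR 12". Section 16.3.1.2 gives both arms the same origin for the primary endpoint: "The interval will start 6 months after therapy start". It defines the event, "Reactivation (=progression in any organs) and death will be considered as events", and the censoring date: "For censored patients the interval will be calculated until the date of the last response evaluation".

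The visit calendar has a different origin. Section 13 is headed "FOLLOW UP INVESTIGATIONS AFTER STOP OF THERAPY". For patients without risk organ involvement it asks for a clinical examination every 6 weeks and laboratory tests every 3 months in the first year after stop, then both every 6 months in years 2 to 5. A footnote lets the later examinations be done "more frequently when clinically indicated".

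For LR 12 patients still on treatment, the table in section 10.3.2 has one row for months 6-12, "during continuation treatment LR 12". It lists an action for each response category but no evaluation interval. Section 9.2.1.3 brings these patients in for vinblastine, "i.v. bolus, day 1 q 3 weeks", but does not call those attendances response evaluations.

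No section puts the two randomised arms on one evaluation calendar from randomisation or therapy start.

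**The concern.** Reactivation is observed only when someone looks for it, and both event dates and censoring dates come from evaluations. If the calendar depends on the arm, the log-rank comparison carries some difference in ascertainment along with the treatment effect. Sparser evaluation dates reactivations later. It also loses some, because a patient who reactivates and then drops out before the next visit is censored at the previous one. The trial is open label and the primary comparison rests on 36 events, so a few shifted events count. The Weibull acceleration factor planned in section 16.3.1.2 concerns the speed of reactivation and depends on the same dates. Analysis cannot recover evaluations that were never scheduled.

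**Working it through.** **Inputs.** Section 16.5.2: 1-year reactivation-free survival 65% (LR 6) and 85% (LR 12), exponential; 36 events; at most 148 patients; loss hazard 0.664 per year; about 6 years of recruitment; 2 years minimum follow-up. Section 16.3: two-sided 5%.

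**The plan's own figure.** HR = ln 0.85 / ln 0.65 = 0.377. Schoenfeld events = 4 × (1.960 + 0.842)² / (ln 0.377)² = 33.0. A five-look two-sided O'Brien-Fleming design with an inner boundary inflates this by about 1.125: 33.0 × 1.125 = 37.2, within 2 of the stated 36. The event target is not in question.

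**Scheduled clinical examinations**, months counted from therapy start (6 weeks is about 1.4 months):

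| Months | LR 6 | LR 12 |
|---|---|---|
| 6-12 | about 4 | not stated: 1 if only at month 12, about 5 if 6-weekly, about 9 if at every treatment visit |
| 12-18 | 4-5 | 4 |
| 18-24 | 1 | 4-5 |
| after 24 | one per 6 months | one per 6 months |

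The arms differ in months 6-12 and 18-24, which are months 0-6 and 12-18 on the primary clock.

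**Events exposed in months 18-24, LR 6.** The reactivation hazard is -ln 0.65 = 0.431 per year. Ignoring loss, the share of patients reactivating is 0.65 - 0.65^1.5 = 0.65 - 0.524 = 12.6%. With loss, the combined hazard is 0.431 + 0.664 = 1.095, and reactivation while still followed is (0.431/1.095) × (e^-1.095 - e^-1.642) = 0.394 × 0.141 = 5.5%. That is about 4 of 74 patients. It is about 17% of the arm's observed reactivations to month 24: 0.055 / [0.394 × (1 - e^-1.642)] = 0.055 / 0.317.

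**Effect on the test.** Simulated as a single fixed log-rank test with 74 patients per arm, uniform accrual and the inputs above. Section 13 examinations count as response evaluations. The common calendar is the LR 6 calendar given to both arms. With 1,500 runs per setting, Monte Carlo error is about 0.6 points for the null rejection rate and about 1 point for power.

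Reactivations found only at visits:

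| LR 12 evaluation, months 6-12 | Null HR (LR 12 / LR 6) | Mean Z | Null rejection | Mean LR 12 events, null | Power |
|---|---|---|---|---|---|
| every 3 weeks | 1.04 | +0.14 | 5.0% | 27.0 | 82% |
| every 6 weeks | 1.03 | +0.10 | 5.0% | 26.8 | 82% |
| only at month 12 | 0.94 | -0.24 | 4.7% | 25.4 | 84% |
| common calendar | 0.99 | -0.02 | 4.4% | 26.3 | 84% |

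Repeat simulations of the same design put total null rejection at 4.4-5.8%, power at 80-84% with the arm-dependent calendars, and power at 83-85% with a common one. The split between tails does move:

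- LR 12 first evaluated at month 12: about 4% of null trials favour LR 12 and about 1.5% favour LR 6.
- LR 12 evaluated every 3 weeks: about 1% favour LR 12 and about 3% favour LR 6.

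Half of reactivations found at once through symptoms: null HR 0.99-1.00 under every calendar, null rejection 5.2-6.0% (common calendar 5.6%), power 82-85% (common calendar 85%).

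**The case against.** Several points weigh against a strong reading, and most of them stand.

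- **Symptoms.** Section 13 allows extra examinations when clinically indicated, and in years 2 to 5 bone radiographs are taken only for suspected lesions. Detection purely by calendar is therefore a worst case, and the asymmetry almost disappears once half of reactivations present between visits.
- **The month-12-only case is unlikely.** LR 12 patients attend every 3 weeks for treatment, and the months 6-12 row in section 10.3.2 presupposes assessment within that window. If they are evaluated at those attendances, the remaining asymmetry works against LR 12 and is conservative for the longer treatment. But the protocol does not say that they are, so the direction stays open.
- **Inflated type I error.** A reader might infer that the plan rejects a true null too often. Total two-sided error stays near 5% under every calendar tried; only its division between the tails changes.
- **Reactivation-free survival estimates.** A reader might infer that the LR 6 curve is badly overstated. A large gap appears only just before the month 24 visit, when detection lag is greatest. Section 16.3.1.2 reports 2- and 3-year rates, which fall at months 30 and 42 from therapy start. The schedules coincide from month 24, so these estimates are less exposed than the log-rank test.
- **Ordinary care and later analysis.** Post-treatment surveillance that starts when treatment ends is normal practice, and an interval-censored sensitivity analysis could sit in an analysis plan that is not shown. Such an analysis could model the detection delay, but it would not supply the missing evaluations or a stated LR 12 interval. The visit schedule is protocol content.

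**Conclusion.** The point holds as a modest, avoidable design weakness. The calendar is tied to an arm-dependent date, the primary clock is not, and nothing in the protocol reconciles the two. At the plan's own rates the worst case (detection only at visits) moves the apparent null hazard ratio to about 0.94-1.04, makes the tails unequal and costs at most a few points of power, which stays at about 80% or above. The 36 events and the sample size are not undermined. The direction cannot be read from the protocol, because it depends on the LR 12 evaluation interval in months 6-12.

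This rests on assumptions that the protocol does not supply: uniform accrual, section 13 examinations counting as response evaluations, the share of reactivations found through symptoms (0% and 50% tried) and the LR 12 interval (three values tried). The simulations used one fixed test, not the group sequential boundaries.

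**What to change.** Reconcile sections 10.3.2, 13 and 16.3.1.2 so that response evaluations for randomised Group 2 patients follow one calendar counted from therapy start (or randomisation), with the same intervals in both arms whether or not therapy is still being given. State the evaluation interval for LR 12 in months 6-12. Name these common evaluations as the source of event and censoring dates in section 16.3.1.2. The choice of interval belongs to the clinical team; the statistical requirement is only that it is stated and equal in both arms.

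The cost is protocol wording plus, if the denser of the two present schedules is kept, a few extra clinical examinations per LR 6 patient in months 18-24 (about 1 now against 4-5 in LR 12). LR 12 patients already attend every 3 weeks in months 6-12. Treatment, sample size and the primary test are unchanged.
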